4.4.3. Exploratory Efficacy Variables

The exploratory efficacy variables include:

- Patterns of failure in patients with local, regional, or distant disease recurrence is measured by descriptive analysis according to the procedures outlined in the protocol.
- Change in estimated costs due to change in surgical plan during screening period versus actual surgical procedure performed after neoadjuvant cemiplimab and change in estimated costs due to the change in post-surgical management plan during screening period versus actual post-surgical management: Costs are estimated based on the latest Physician Fee Schedule published by Centers for Medicare & Medicaid Services. The difference between cost of planned surgery versus cost of actual surgery that is performed is then calculated. A cost of zero is assigned to patients for whom the post-surgical management plan is observation. For patients who receive adjuvant therapy, the actual cost will be estimated.
- Health-related quality of life (HRQoL) is measured by the EORTC QLQ-C30. The global health status, functioning scales (physical, role, emotional, cognitive, and social), patient-reported symptom scales (fatigue, nausea and vomiting, pain) and

single items (appetite loss, dyspnea, insomnia, constipation, diarrhea, and financial impact) will be computed using QLQ-C30 scoring procedures.

4.5. Safety Variables

Patient safety will be assessed through the collection of reported adverse events (AEs), clinical laboratory data, vital signs, ECG, and physical exam.

The observation period will be divided into three segments: pre-treatment, on-treatment and post-treatment.

- The pre-treatment period is defined as the time from signing the ICF to before the first dose of study drug.
- The treatment period is defined as the time from the day of first dose of neoadjuvant cemiplimab to the day of the last dose of neoadjuvant cemiplimab plus 90 days or to 1 day before patients receive their first dose of adjuvant cemiplimab or another anticancer systemic therapy, whichever is earlier.
- The post-treatment period is defined as the time starting one day after the end of on treatment period.

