8.3. Study Drug Discontinuation

This section provides guidance on management of AEs that are suspected to be related to study drug. The general approach to missed doses of study drug (eg, due to AEs) is “time marches on.” Missed doses of study drug will not be made up, unless ≤ 3 days from the scheduled date.

The investigator may choose to hold study drug at his/her clinical judgment regarding the safety of an individual patient, even if hold criteria are not formally met per protocol.

Adverse event severity is to be graded according to the National Cancer Institute Common Terminology Criteria for Adverse Events (NCI-CTCAE) version 5 (Section 10.5.1).

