- Patients who receive adjuvant radiation therapy or enter observation only during Part 2 of the study will follow a parallel imaging schedule as described in [Section 9.1.6](#).
- The window for treatment visits is ± 3 days. In the event of a missed dose, patients will not be allowed to receive the scheduled cemiplimab dose outside of this window. Any missed doses will result in a reduction in the total number of allowable doses that may be administered.

Table 2: Schedule of Events for Screening, Neoadjuvant Cemiplimab, and Surgery (Part 1 of the Study)

Study Procedure	Screening/ Baseline ¹	Cemiplimab Treatment				Surgery	EOT1 (or Early Termination) ³
		1	22±3	43±3	64±3		
Visit Days	-28 to -1					85 (75 to 100)	30 days ± 10 after surgery
Informed Consent ²	X						
Clinical Assessments							
Medical History/Oncology History	X						
Complete Physical Examination and ECOG PS	X						X
Limited Physical Examination		X	X	X	X		
Vital Signs and Weight	X	X ⁴	X ⁴	X ⁴	X ⁴		X
Height	X						
12-Lead ECG	X						X
Laboratory Tests							
Hematology ⁵	X	X	X	X	X		X
Blood Chemistry ⁵	X	X	X	X	X		X
Pregnancy Test for WOCBP ⁶	X	X	X	X	X		X
Urinalysis	X						X
HBV, HCV, HIV	X						
INR, aPTT ⁷	X					X	
TSH (with reflex T3, free T4) ⁸	X						X
Treatment							
Cemiplimab 350 mg IV Q3W		X	X	X	X		
Surgery ⁹						X	
Response Assessment							
CT/MRI ¹⁰	X			X		X	X
Digital Photography ¹⁰	X			X		X	
Tumor Biopsy ¹¹	X		X				
Treatment Management Plan Assessment ¹²	X				X		
PD/Biomarker Analysis							
PBMC Immune Monitoring Sample		X	X				
Plasma ctDNA Sample	X						X
Whole Blood Genomic DNA (mandatory)	X ¹³						
Whole Blood Genomic DNA (optional sub-study)		X ¹⁴					
Immunogenicity							
ADASample ¹⁵		X				X	X
Patient Reported Outcomes							
EORTC-QLQ-C30 ¹⁶	X					X	

Other Assessments	
Concomitant Medications	← continuous monitoring →
Adverse Events	← continuous monitoring →

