10.5.2. Evaluation of Causality

Relationship of Adverse Events to Study Drug:

The relationship of AEs to study drug will be assessed by the investigator and will be a clinical decision based on all available information. The following question will be addressed:

Is there a reasonable possibility that the AE may have been caused by the study drug?

The possible answers are:

- **Not Related:** There is no reasonable possibility that the event may have been caused by the study drug
- **Related:** There is a reasonable possibility that the event may have been caused by the study drug

The investigator should justify the causality assessment of each SAE.

A list of factors to consider when assessing the relationship of AEs to study drug is provided below. Please note that this list is not exhaustive.

Is there a reasonable possibility that the event may have been caused by the study drug?

No:

- due to external causes such as environmental factors or other treatment(s) being administered
- due to the patient's disease state or clinical condition
- do not follow a reasonable temporal sequence following the time of administration of the dose of study drug
- do not reappear or worsen when dosing with study drug is resumed
- are not a suspected response to the study drug based upon preclinical data or prior clinical data

Yes:

- could not be explained by environmental factors or other treatment(s) being administered
- could not be explained by the patient's disease state or clinical condition
- follow a reasonable temporal sequence following the time of administration of the dose of study drug
- resolve or improve after interruption or discontinuation of study drug
- reappear or worsen when dosing with study drug is resumed
- are known or suspected to be a response to the study drug based upon preclinical data or prior clinical data

Causality to adjuvant surgery:

- Related:
 - The AE follows a reasonable temporal sequence from a protocol specified procedure and cannot be reasonably explained by the nature of the reaction, patient's clinical (eg, disease under study, concurrent diseases, concomitant medications), or other external factors.
- Not Related:
 - The AE does not follow a reasonable sequence from a protocol specified procedure or can be reasonably explained by the nature of the reaction, patient's clinical state (eg, disease under study, concurrent diseases, and concomitant medications) or other external factors.

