11.5.5.1. Adverse Events

Definitions

For safety variables, 3 observation periods are defined:

- The pretreatment period is defined as the time from signing the ICF to before the first dose of study drug.
- The treatment period is defined as the time from the day of first dose of neoadjuvant cemiplimab to the day of the last dose of neoadjuvant cemiplimab plus 90 days or to 1 day before patients receive their first dose of adjuvant cemiplimab or another anticancer systemic therapy, whichever is earlier.
- The post-treatment period is defined as the time starting one day after the end of on-treatment period.

Treatment-emergent AEs (TEAEs) are defined as AEs that developed or worsened during the on-treatment period and any treatment-related AEs that occur during the post-treatment period but prior to patients receiving their first dose of cemiplimab as adjuvant therapy or another anticancer systemic therapy.

Adverse events (AEs) during adjuvant cemiplimab will be summarized separately from AEs emerging in the neoadjuvant period. AEs will be collected from the date of first dose of adjuvant cemiplimab up to 90 days following the last dose. Additionally, any treatment-related AEs identified more than 90 days following the last dose will be captured.

Analysis

All AEs reported in this study will be coded using the currently available version of the Medical Dictionary for Regulatory Activities (MedDRA[®]). Coding will be to lowest level terms. The verbatim text, the preferred term, and the primary system organ class (SOC) will be listed.

Summaries of all TEAEs will include:

- The number (n) and percentage (%) of patients with at least 1 TEAE by SOC and preferred term
- TEAEs by severity (according to the grading scale outlined in Section 10.5.1), presented by SOC and preferred term

- TEAEs related to treatment, presented by SOC and preferred term
- Treatment-emergent AESIs (defined with a preferred term or a prespecified grouping)

Deaths and other SAEs will be listed and summarized.

Treatment-emergent adverse events leading to permanent treatment discontinuation will be listed and summarized.

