4.5.1. Adverse Events and Serious Adverse Events

An AE is any untoward medical occurrence in a patient administered a study drug which may or may not have a causal relationship with the study drug. Therefore, an AE is any unfavorable and unintended sign (including abnormal laboratory finding), symptom, or disease which is temporally associated with the use of a study drug, whether or not considered related to the study drug.

An AE also includes any worsening (ie, any clinically significant change in frequency and/or intensity) of a pre-existing condition that is temporally associated with the use of the study drug.

The investigator (or designee) will seek information on AEs at each patient contact and record all AEs that occur from the time the informed consent is signed until 90 days after the last dose of study drug. Prior to initiation of study drug, only the following categories of AEs should be reported on the AE eCRF:

- SAEs
- Non-SAEs associated with a protocol-mandated intervention (eg, AEs related to an invasive procedure such as a biopsy)

Other AEs that occur prior to first treatment should be reported on the medical history eCRF.

All AEs after initiation of study drug and until 90 days after the last dose of study drug, regardless of relationship to study drug, will be reported on the AE eCRF. Additionally, any SAE or other AE of concern that the investigator believes may be related to study drug and that occurs later than 90 days after last study drug should be reported.

Pre-treatment AEs are defined as AEs that developed or worsened during the pre-treatment period.

Treatment-emergent AEs (TEAEs) are defined as AEs that developed or worsened during the on-treatment period and any treatment-related AEs that occur during the post-treatment period but prior to patients receiving their first dose of cemiplimab as adjuvant therapy or another anticancer systemic therapy.

Post-treatment AEs are defined as AEs that developed or worsened during the post-treatment period and are not considered drug related by the investigator.

All adverse events are to be coded using Medical Dictionary for Regulatory Activities (MedDRA).

The severity of AEs (including test findings classified as AEs) will be graded using the NCI-CTCAE v5. Adverse events not listed in the NCI-CTCAE v5 will be graded according to the following scale (Table 2):

Table 2: Grading System for Adverse Events Not Listed in NCI-CTCAE

Grade	Severity	Description

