5.7.4. Analysis of 12-Lead ECG

ECG parameters will be summarized by Baseline and change from Baseline to each scheduled assessment time with descriptive statistics.

ECG status (ie, normal, abnormal, not clinically significant, and abnormal clinically significant) will be reported. Shift tables from baseline to worst post-baseline findings (normal, abnormal not clinically significant, and abnormal clinically significant) during on-treatment period will be generated.

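### When the last neoadjuvant dose was dose 1 or 2 and surgery was not brought forward, the 90-day on-treatment period can close before the EOT1 visit

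*SAP*

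**What the plan says.** **On-treatment period.** SAP 4.5 and protocol 11.5.5.1 give the same definition. The period starts at the first neoadjuvant dose and runs "to the day of the last dose of neoadjuvant cemiplimab plus 90 days", or to the day before adjuvant cemiplimab or another systemic anticancer therapy if that comes first.

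**AE collection.** SAP 4.5.1 and protocol 10.4.1 require recording of "All AEs after initiation of study drug and until 90 days after the last dose of study drug, regardless of relationship to study drug". Beyond that they ask only for "any SAE or other AE of concern that the investigator believes may be related to study drug and that occurs later than 90 days". Protocol 10.4.2 applies the same limit to SAEs. Protocol 8.3.5 and 9.1.5.1 set 90 days of AE follow-up for patients who stop neoadjuvant drug for progression or toxicity, and 9.1.5.1 bars those patients from adjuvant cemiplimab.

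**Surgery and EOT1.** Table 2 puts surgery on day 85 (75 to 100) and EOT1 at "30 days ± 10 after surgery". A hold does not shift the calendar: "Missed doses of study drug will not be made up, unless ≤ 3 days from the scheduled date" (protocol 8.3).

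**Outputs tied to the period.** TEAEs are AEs arising in the on-treatment period, plus later drug-related AEs up to the start of adjuvant cemiplimab or other systemic therapy (SAP 4.5.1). The worst-value laboratory tables (SAP 5.7.2) and the physical-examination summary (SAP 5.7.5) are confined to the on-treatment period. For ECG, "Shift tables from baseline to worst post-baseline findings (normal, abnormal not clinically significant, and abnormal clinically significant) during on-treatment period will be generated" (SAP 5.7.4).

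**The concern.** The safety window follows the last dose, while the operation and the visit after it follow the study calendar. If dosing ends early and surgery stays in its calendar window, the safety window can close shortly after the operation, or before it. Safety is a secondary objective and endpoint, and post-operative complications are a natural question in a neoadjuvant trial. Protocol 10.5.2 has investigators judge whether an AE is due to surgery, asking whether "The AE follows a reasonable temporal sequence from a protocol specified procedure". An event judged due to surgery and not to drug is exactly the kind that leaves the TEAE count once the window closes. Because the cut depends on how many doses were given, it falls on patients who had to stop or hold treatment early.

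**Working it through.** **Inputs.** Dose days 1, 22, 43 and 64, ±3 after the first (protocol 6.1.2). Surgery day 75 to 100, nominal 85, and EOT1 20 to 40 days after surgery, nominal 30 (Table 2). On-treatment limit: last dose + 90 days (SAP 4.5).

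**1. The plan's own date.** Last planned dose + 21 days = 64 + 21 = day 85, which matches Table 2.

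**2. EOT1 range.** Earliest 75 + 20 = day 95; nominal 85 + 30 = day 115; latest 100 + 40 = day 140.

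**3. Window end by last dose.** Window end = last dose day + 90. Post-operative cover = window end − surgery day. The last column is the share of the 26 × 21 = 546 allowed combinations of surgery day and EOT1 day in which EOT1 falls inside the window. It counts calendar combinations and does not forecast how often each occurs.

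| Last dose | Window ends | vs nominal EOT1 (115) | Cover, surgery day 85 | Cover, surgery day 100 | EOT1 inside |
|---|---|---|---|---|---|
| Dose 1 (day 1) | 91 | 24 days before | 6 days | −9 days | 0% |
| Dose 2 (day 22) | 112 | 3 days before | 27 days | 12 days | 31% |
| Dose 3 (day 43) | 133 | 18 days after | 48 days | 33 days | 95% |
| Dose 4 (day 64) | 154 | 39 days after | 69 days | 54 days | 100% |

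Moving dose 2 within ±3 days puts the window end at day 109 to 115, a nominal shortfall of 6 to 0 days. For dose 3 the window end is day 130 to 136.

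**4. General rule.** Nominal EOT1 is surgery + 30. It falls outside when surgery + 30 > last dose + 90, that is, when surgery is more than 60 days after the last dose. For dose 1 this means after day 61, so always in the surgery window. For dose 2 it means after day 82. For dose 3 (after day 103) and dose 4 (after day 124) it cannot happen inside the surgery window.

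**5. Surgery brought forward.** With surgery at last dose + 21, EOT1 falls at last dose + 41 to + 61. The window then stays open 90 − 61 = 29 to 90 − 41 = 49 days beyond EOT1, whatever the dose count.

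**6. Can the affected patient arise?** Yes. Appendix 2 sets corticosteroid tapers of at least a month for several irAEs, and protocol 8.3.3.2 ties resumption to the taper. A hold starting on day 43 with a taper of about 30 days runs to about day 73, past the last dosing visit (64 + 3 = day 67). The last dose is then day 22. Such a patient need not have met discontinuation criteria, so the calendar surgery window still applies.

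**7. What drops out after the window closes.**
- AEs judged unrelated to drug become post-treatment AEs (SAP 4.5.1). SAP 5.7.1 plans no summary of these. Protocol 11.5.5.1 does promise that deaths and SAEs will be listed and summarized, without naming a period, but that helps only if they were collected.
- Permanent discontinuers cannot take adjuvant cemiplimab, so no later dose extends collection, and those AEs are not required. The same applies to a patient on hold who then has radiation or observation.
- In Table 2, ECG and TSH appear only at screening and EOT1. No later schedule contains an ECG. TSH returns in Table 3, which applies in full only to patients on adjuvant cemiplimab, and in Table 4; permanent discontinuers follow imaging only (9.1.5.1).

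**The case against.** A reader might infer that every patient who stops or holds dosing early loses post-operative safety data. The documents do not support that.

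- **Timing of surgery.** Protocol 8.3.5 says that patients who stop permanently for progression or toxicity go to surgery, and Table 2 footnote 9 asks for surgery 21 days after the last dose. Anyone treated that way is covered (step 5). This stands. It does not remove the gap, because 8.3.5 gives no date, 6.1.2 only permits earlier surgery, and footnote 9 also keeps the day 75 to 100 window. The two parts of footnote 9 agree only for a last dose between 75 − 21 = day 54 and 100 − 21 = day 79, so not for doses 1 to 3.
- **Holds.** A patient who missed a middle dose but received dose 4 is covered to day 154. This stands.
- **Collection.** The 90 days count from the last dose of study drug, adjuvant doses included. A patient on hold who later takes adjuvant cemiplimab still has post-operative AEs recorded. For that patient the loss is in classification only.
- **Laboratory and ECG data.** By-visit change-from-baseline summaries (SAP 5.7.2, 5.7.4) are not limited to the on-treatment period and keep EOT1.
- **Bias.** It is tempting to say that the drug's safety profile will look too favourable. Drug-related AEs after the window stay TEAEs, and missing relatedness is imputed as related (SAP 6.3). Only events judged unrelated leave the count.
- **Contradiction.** The continuous-monitoring entry in Table 2 might be read as contradicting the 90-day rule. Table 4 has the same entry across three years of follow-up, so it cannot set an end date. Protocol 10.5.2 says how to judge causality, not for how long to collect.

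**Conclusion.** The point holds for a defined group: last neoadjuvant dose at dose 1 or 2, and surgery more than about 60 days after it. After one dose, every EOT1 that the surgery window allows is outside, and with surgery on day 100 the window closes 9 days before the operation. After two doses the nominal EOT1 is outside by 3 days, with 27 post-operative days already covered. After three doses EOT1 is nearly always inside, and after four it always is.

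In the affected group the loss is limited to post-operative AEs judged unrelated to drug and to the place of EOT1 findings in the on-treatment worst-value, ECG-shift and physical-examination tables. Where no further cemiplimab is given, those AEs may also go uncollected, and no later analysis can recover them.

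The documents give no early-stop rate. On an assumed 5% to 15% of 76 patients receiving two doses or fewer, 76 × 0.05 = 3.8 and 76 × 0.15 = 11.4, so about 4 to 11. This is an upper bound: it still counts patients operated on early, patients never operated on, and two-dose patients whose EOT1 falls by day 112. The primary endpoint is unaffected. This is a cheap improvement.

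**What to change.** Define the end of Part 1 AE collection and of the on-treatment period as the later of (a) last neoadjuvant dose + 90 days and (b) the EOT1 visit. Keep the cut-off at the day before adjuvant cemiplimab or other systemic therapy. Where no EOT1 visit takes place, (a) applies. Make the change in protocol 8.3.5, 9.1.5.1, 10.4.1, 10.4.2 and 11.5.5.1 and in SAP 4.5 and 4.5.1 together; changing only some of them would create new contradictions.

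With surgery on day 85 and nominal EOT1, the end moves from day 91 to 115 after one dose and from day 112 to 115 after two. It stays at day 133 or 154 after three or four. The first adjuvant dose comes 3 weeks (±3 days) after EOT1, so the retained cut-off does not remove that visit.

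Separately, reconcile the passages on surgery timing after early stopping: protocol 6.1.2, 8.3.5 and both parts of Table 2 footnote 9. Which rule should apply is a clinical decision for the sponsor.

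Cost: wording in both documents and a short extension of AE recording for a few patients. EOT1 already takes place, so no visit is added. The downside is that a few more unrelated post-operative AEs count as TEAEs. A SAP change alone would repair the tables but not the missing collection.

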6.1.3. Treatment in Part 2 (Adjuvant)

Part 2 of the study will begin following surgery. Patients will have the option to receive cemiplimab treatment (350 mg IV Q3W) for up to 48 weeks (16 doses) or until unacceptable toxicity, disease recurrence, or withdrawal of consent. The first dose of adjuvant cemiplimab will occur at 3 weeks (± 3 days) after end of treatment in Part 1 (EOT1). During this part of the study, patients will undergo additional evaluation approximately every 15 weeks. Patients will be evaluated in clinic prior to each cemiplimab treatment and will undergo clinical and imaging assessment during each evaluation visit. At the discretion of the investigator, patients may alternatively receive adjuvant radiation therapy or enter an observation-only period. These patients will be evaluated for disease recurrence by imaging, approximately every 15 weeks.

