8.7.2. Permitted Medications and Procedures

The following medications and procedures will be permitted, under the following conditions:

- Any medication required to treat an AE and/or irAE, including systemic corticosteroids
- Systemic corticosteroids for physiologic replacement (even if >10 mg/day prednisone equivalents)
- A brief course of corticosteroids for prophylaxis or for treatment of non-autoimmune conditions
- Oral contraceptives, hormone-replacement therapy, or other maintenance therapy may continue
- Acetaminophen at doses ≤ 2 g/day
- Surgical resection of pre-malignant lesions or basal cell carcinoma (BCC) lesions
- Other medications and procedures may be permitted on an individual basis by the investigator and in consultation with the sponsor
- Radiation therapy (with concurrent anti-cancer cytotoxic chemotherapy therapy and/or epidermal growth factor receptor-directed therapy) is permitted in the adjuvant portion of the study, at the discretion of the investigator. Such patients will be followed for disease recurrence but will not receive further cemiplimab on study.

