5.7.1. Adverse Events

Summaries that include frequencies and proportions of patients reporting AEs will include the PTs and the SOCs.

Summaries of all TEAEs will include: TEAEs, Treatment related TEAEs, Serious TEAEs, AESI, immune-related AEs (irAE), and IRR. For TEAEs, the following will be summarized:

- The number and proportions of patients reporting at least 1 TEAE, presented by SOC and PT
- TEAEs by severity, presented by SOC and PT

- TEAEs related to treatment, presented by SOC and PT
- TEAEs leading to permanent treatment discontinuation, presented by SOC, PT
- TEAEs leading to death, presented by SOC and PT
- IRRs by SOC, PT and NCI-CTCAE grade
- AESIs by SOC, PT and NCI-CTCAE grade
- Treatment-emergent irAEs by SOC, PT and NCI-CTCAE grade

For each TEAE summary presented by SOC and PT, the summary table will be sorted by decreasing frequency of SOC and PT. For TEAE summary presented by PT, the summary table will be sorted by decreasing frequency of PT.

Adverse events (AEs) during adjuvant cemiplimab will be summarized separately from AEs emerging in the neoadjuvant period. AEs will be collected from the date of first dose of adjuvant cemiplimab up to 90 days following the last dose.

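### Adjuvant radiation given alone does not close the neoadjuvant on-treatment period, so AEs starting after radiation but within 90 days of the last neoadjuvant dose count as neoadjuvant TEAEs

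*SAP*

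**What the plan says.** SAP 4.5 starts the treatment period at the first neoadjuvant dose and runs it "to the day of the last dose of neoadjuvant cemiplimab plus 90 days", with an early stop: "or to 1 day before patients receive their first dose of adjuvant cemiplimab or another anticancer systemic therapy, whichever is earlier". Protocol 11.5.5.1 has the same rule, stopping one "day before patients receive their first dose of adjuvant cemiplimab or another anticancer systemic therapy, whichever is earlier". Neither mentions radiation.

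SAP 4.5.1 makes everything in that period treatment-emergent, whatever its cause: "Treatment-emergent AEs (TEAEs) are defined as AEs that developed or worsened during the on-treatment period". A further clause adds treatment-related AEs that occur later, until adjuvant cemiplimab or another systemic anticancer therapy begins. Collection matches this: "All AEs after initiation of study drug and until 90 days after the last dose of study drug, regardless of relationship to study drug" goes on the AE form.

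Radiation is one of three routes in Part 2. Protocol 6.1.3 says: "At the discretion of the investigator, patients may alternatively receive adjuvant radiation therapy or enter an observation-only period". Protocol 8.7.2 also allows it with systemic agents: "Radiation therapy (with concurrent anti-cancer cytotoxic chemotherapy therapy and/or epidermal growth factor receptor-directed therapy) is permitted in the adjuvant portion of the study".

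Only one Part 2 treatment gets its own AE summary, in SAP 5.7.1: "Adverse events (AEs) during adjuvant cemiplimab will be summarized separately from AEs emerging in the neoadjuvant period". No section flags, excludes or separately tabulates AEs that begin after radiation starts.

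**The concern.** The early-stop rule keeps the toxicity of the next anticancer treatment out of the neoadjuvant tables. It does so for adjuvant cemiplimab and for systemic agents but omits radiation alone, which the protocol itself offers. As written, two patients given the same radiation are handled differently if only one also receives a concurrent systemic agent. For that patient the period stops; for the other it continues to the 90-day limit.

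Safety of neoadjuvant cemiplimab is a secondary objective, and there is no control arm to absorb toxicity from another source. The absolute TEAE percentages are the result. Part of what they show would depend on how often, and how soon, investigators choose radiation. Some terms could come from either treatment: Protocol 3.2.3 describes skin effects of radiation, while Protocol Appendix 2 lists dermatitis and erythema among immune-related skin toxicities.

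**Working it through.** No figure in the plan depends on this rule, so there is nothing to reproduce. The check is date arithmetic on the protocol's visit windows.

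**Inputs**
- Last planned neoadjuvant dose, L: day 64 ± 3, so 61 to 67 (Protocol 6.1.2).
- Surgery, S: day 85, window 75 to 100 (Protocol 6.1.2, Table 2).
- EOT1, V days after surgery: 30 ± 10 (Protocol Table 2).
- Week 0 of Part 2, W days after EOT1: 21 ± 3 (Protocol 9.1).
- Time limit: L + 90 (SAP 4.5).
- Radiation start, R: not stated. Part 2 consent must precede any adjuvant treatment (Protocol 6.1.7) and should be taken at EOT1 (Table 3, footnote 4). I therefore assume two starts, EOT1 and week 0.

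**Formulas**
- End of period: E = L + 90.
- Radiation start: R = S + V (EOT1) or R = S + V + W (week 0).
- Overlap in days = E − R + 1, or 0 if negative.

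**Nominal timing**
- E = 64 + 90 = 154.
- EOT1 start: R = 85 + 30 = 115; overlap = 154 − 115 + 1 = **40 days**.
- Week 0 start: R = 85 + 30 + 21 = 136; overlap = 154 − 136 + 1 = **19 days**.

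**Limits of the allowed windows, four doses given**
- EOT1 start, shortest: E = 61 + 90 = 151, R = 100 + 40 = 140, overlap 12.
- EOT1 start, longest: E = 67 + 90 = 157, R = 75 + 20 = 95, overlap 63.
- Week 0 start, shortest: E = 151, R = 100 + 40 + 24 = 164, overlap 0.
- Week 0 start, longest: E = 157, R = 75 + 20 + 18 = 113, overlap 45.

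These limits let each window vary freely. The longest pairs a day 67 dose with day 75 surgery, 8 days apart, although Table 2 footnote 9 asks for 21 days. They are bounds, not typical values.

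**Shorter course:** last dose day 43, surgery day 85. E = 43 + 90 = 133. Overlap is 133 − 115 + 1 = 19 days from EOT1, and 0 from week 0 because 136 is after 133.

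**Period end by Part 2 route, nominal timing**
- Adjuvant cemiplimab: day 135.
- Observation: day 154.
- Radiation alone: day 154.
- Radiation with a systemic agent: the day before that agent starts, if before day 154.

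**Laboratory tables:** Table 3 footnote 1 says Part 2 laboratory assessments do not apply to radiation patients. Their last scheduled sample is at EOT1 (day 115). Their next scheduled visit is week 15, imaging only, at day 136 + 105 = 241, well past day 154. Only unscheduled values, which SAP 6.4 admits to worst-value summaries, could fall after radiation starts.

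**Effect on a rate:** the tables count patients with at least one event. If all 76 planned patients are dosed, one irradiated patient with a new event moves a category by 1/76 = 1.3 percentage points. A patient who already had that event moves its any-grade count by nothing. The documents give no number irradiated, so this cannot be taken further.

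**The case against.** The strongest defence is that a full 90-day, all-cause window is conservative and deliberate. Surgical AEs already fall inside it, and Protocol 8.3.3.1 warns that immune-related events may appear months after the last dose. Stopping at radiation would give those patients less observation than observation-only patients and would drop late events judged unrelated. That cost is real and argues for showing both versions. It does not explain the omission, because the plan already departs from a plain 90-day window when other anticancer treatments start.

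The second defence is causality. Protocol 10.5.2 names other treatment being given as grounds for calling an AE not related, and related TEAEs are tabulated separately. This stands for the related tables, apart from terms that could fit either treatment and SAP 6.3's rule that missing causality is imputed as related. It does nothing for the all-cause, severity and serious tables.

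Third, a separate radiation table would not match the adjuvant-cemiplimab one. That one runs to 90 days after the last adjuvant dose, whereas all-cause collection for radiation patients stops 90 days after the last neoadjuvant dose. This also stands and limits what the extra table can show.

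A reader might infer a large inflation: if 10% to 30% of 76 patients (8 to 23) had radiation alone, a category such as skin toxicity might seem to rise by 10 to 30 points. The documents do not support that. The share is a guess, and the figure is a ceiling that needs every such patient to have a first event in that category before the window closes.

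**Conclusion.** The gap is real and appears identically in both documents, so it is an analysis choice and not a conflict between protocol and SAP. AEs starting after radiation alone begins and by the 90-day limit (nominal day 154; 151 to 157 for a four-dose course) count as neoadjuvant TEAEs in the all-cause, severity and serious tables. The nominal exposure is 40 or 19 days, on the assumption that radiation starts at EOT1 or week 0. It can be nil for a later start or a shorter course.

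A reader might also infer that all radiation toxicity is counted, or that the worst-laboratory and treatment-related tables are equally affected. Toxicity with onset after the limit is post-treatment and enters only if judged related to cemiplimab. Scheduled laboratory tests do not fall in the overlap under the assumed starts, and the causality rule largely protects the related tables. The primary endpoint and sample size are untouched. This is a cheap improvement to a descriptive safety analysis, and its effect on TEAE rates cannot be computed from the documents.

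**What to change.** In SAP 4.5, present the neoadjuvant TEAE summaries with the period also ending 1 day before the first fraction of adjuvant radiation. Tabulate AEs starting on or after that date separately. If the sponsor prefers to keep the full 90-day table, show this version beside it. At nominal timing the period for a radiation patient would then end on day 114 (EOT1 start) or day 135 (week 0 start) instead of day 154, and the overlap would be zero.

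The radiation start date is already captured on the eCRF (Protocol 5.2.2.2), so no new data are needed. The existing clause in SAP 4.5.1 keeps later treatment-related AEs as TEAEs. The departure from Protocol 11.5.5.1 can be recorded in SAP 1.2.4, and SAP section 1 allows revision before database lock.

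The cost is some wording and one extra set of tables. There are three downsides to state with the output:
- Radiation patients get a shorter all-cause window.
- Late events judged unrelated move to the separate table.
- That table covers only the days up to 90 days after the last neoadjuvant dose, so it should not be read as a full account of radiation safety.
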